#### 6.2 Exclusion criteria

- 1. Patients unable to tolerate synovial biopsy or in whom this is contraindicated including patients on anti-coagulants (e.g. warfarin). Patients on short-acting direct oral anticoagulant agents can be considered when anti-coagulant can be temporarily stopped, in line with local guidelines for procedures with a low risk of bleeding, taking into account the individual thromboembolic risk. Oral anti-platelet agents are permitted.
- 2. Patients in whom there is no suitable joint for biopsy.

- 3. Hypersensitivity to the active substance or to any of the excipients of abatacept or methotrexate, or any other contraindications to the study medications, as per the current SmPC.
- 4. History of or current primary inflammatory joint disease or primary rheumatological autoimmune disease other than RA (if secondary to RA, then the patient is still eligible).
- 5. Prior exposure to any biologic/targeted DMARDs for RA
- 6. Treatment with any investigational agent ≤ 8 weeks prior to baseline or < 5 half-lives of the investigational drug (whichever is the longer)
- 7. Intra-articular or parenteral corticosteroids, or oral prednisolone more than 10mg/d or equivalent ≤ 4 weeks prior to screening visit.
- 8. Patients with a serious underlying medical disorder (e.g., end stage renal disease).
- 9. Active infection
- 10. Subject has a history or known presence of recurrent or chronic infection (eg, hepatitis B virus [HBV], hepatitis C virus [HCV], human immunodeficiency virus HIV]; recurrent urinary tract infections are allowed.
- 11. Subjects testing positive for acute or chronic hepatitis A, B, or C, unless they are indicative of prior hepatitis B vaccination or cured hepatitis A or B and accompanied by normal liver transaminase values.
- 12. Septic arthritis of a native joint within the last 12 months
- 13. Septic arthritis of a prosthetic joint within 12 months or indefinitely if the joint remains in situ
- 14. Latent TB infection unless they have completed adequate antibiotic prophylaxis
- 15. Receipt of live vaccine <3 months prior to first dose of study medication
- 16. Major surgery in 3 months prior to first dose of study medication
- 17. Presence of a transplanted organ (with the exception of a corneal transplant >3 months prior to screening).
- 18. Known recent substance abuse (drug or alcohol).
- 19. Patients currently recruited to other clinical trials or taking part in a CTIMP study in the previous 4 months.

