# 7.0 Study Schedule

7.1 Schedule of treatment for each visit

# 7.2 Schedule of assessment (in diagrammatic format)

Visit number	1	2 (m)	3	4	5	6	7	Post treatment visit/call
Timeline (weeks)	-6 to -1	-3 to -1	0	4	8	12	16	30 or more days after visit 7
Deviation window (days from scheduled visit)		N/A		+/- 7 days	+/- 7 days	+/- 7 days	+/- 7 days	N/A
Visit type	Screening	Biopsy & Randomisation (m)	Baseline	Treatment Phase				Follow up
ENROLLMENT PROCEDURES								
Informed Consent	Х							
Inclusion and Exclusion Criteria	х							
Demographics	Х							
Medical History (f)	Х							
MEDICAL PROCEDURES								
Concomitant Medication review	x	Х	x	x	x	x	x	
RF & CCP (a)	Х							

ACR Criteria	X							
Pregnancy test (k)	Х		Х	Х	Х	Х	Х	
Chest X-ray (j)	Х							
ECG	Х							
Hepatitis serology, HIV, IGRA (i)	x							
Physical Examination	Х		Х	Х	Х	Х	Х	
Cardiovascular risk profile	Х							
Weight and Height	Х		Х	Х	Х	Х	Х	
Vital Signs (BP, pulse, temp.)	х		х	х	х	х	x	
Haematology, biochemistry panel, ESR, CRP (b)(c)	х		х	х	х	х	x	
DISEASE ACTIVITY ANALYSIS								
Joint Assessment (66/68) (I)	X		X	Х	Х	Х	Х	
X-ray Hands & Feet (h)			X				X	
CDAI	X		X	Х	Х	Х	Х	
DAS28	X		X	Х	Х	Х	Х	
VAS Pain Score	X		X	Х	Х	Х	Х	
HAQ Questionnaire			Х	Х	Х	Х	Х	
TREATMENT PROCEDURES								
Randomisation (g)		Х						
Commencement of randomised treatment			x					
Dispensing of randomised treatment			x	x	х	х		
Adverse Events		Х	Х	Х	Х	Х	Х	Х

Study Bloods	X		Х	Х	Х	Х	
Ultrasound (d)	X (d)					X (d)	
Pre-biopsy Assessment	Х					X (e)	
Synovial Biopsy (e)	X					X (e)	
Post-biopsy Assessment		Х					X (e)
Stool collection (optional)	Х		Х			X	
Urine collection (optional)	X		Х			Х	
Saliva collection (optional)	Х		Х			X	
PATIENT REPORTED OUTCOMES							
FACIT-fatigue Questionnaire		x	x		x	x	
SF-36		Х	Х		Х	Х	
Epworth Sleepiness scale		Х	Х		Х	Х	
EQ-5D-5L		Х	Х		Х	Х	

a. RF/CCP tests should be performed unless these tests have been done previously and do not need repeating as per local guidelines

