b. At screening visit - routine blood tests do not need to be taken if the patient has already had all routine blood tests performed within 3 weeks of the screening visit. At biopsy visit – routine bloods do not need to be taken if the patient has already had routine bloods performed at the screening visit and within 3 weeks of the biopsy visit.

c. ESR, CRP, Haematology (Hb, Haematocrit, WBC, platelet count, neutrophils, lymphocytes, Red blood cell count, Mean cell haemoglobin, Mean cell volume), Biochemistry (Urea, sodium, Creatinine, potassium, ALT, AST).

d. The US assessment at visit 2 will also include the joint selected for biopsy to ensure that there is sufficient thickening to meet the following inclusion criterion: selected joint for biopsy must be a minimum grade 2 synovial thickening, as assessed at the biopsy visit. This is essential for all patients participating in the trial. Full ultrasound assessments may be optional at some participating sites and should include a full set of MCPs and wrist joints-please refer to the ultrasound manual.

e. Assessment and feasibility at visit 7 will be performed. Patients will be asked to consent or opt out. Synovial fluid should also be collected, where possible. Visit 2 biopsy is compulsory for participation in the study. If a participant does not undergo a biopsy at visit 2 for any reason, they will be withdrawn from the study.

f. Including covid-19 history/vaccine status, allergies, and 3TR Disease & other Specific Co-Morbidities.

g. Randomisation will be performed by the central coordinating office on completion of visits 1 and 2 and on receipt of the biopsy at the central laboratory.

h. Alternatively; X-ray of hands and feet may be performed at visit 2 prior to the biopsy. Plain X-rays of hands and feet do not need to be taken if the patient has already had them done within 8 weeks of the baseline visit, as per the imaging manual.

i. Hepatitis B, TB (IGRA), Hepatitis C, and HIV screening must be performed unless it has been done in the preceding 3 months of the screening visit or in line with local practice.

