#### 7.5 Study assessments

All trial activities and the visits at which they should be undertaken are documented in the "Schedule of Assessments" table.

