#### 7.5.1 Screening procedures (visit 1)

During the screening visit, written informed consent will be obtained from all patients by the Principal investigator or his/her designee before any protocol-specific procedure is performed. Study details, risks and benefits will all be reviewed and patients will be encouraged to ask questions and clarify any concerns. Demographic data (including age, assigned sex at birth and race) and medical history will be obtained. Patients, both men and women, will be reminded to use an acceptable and effective method of contraception during the study period and the appropriate time period after stopping study treatment. Patients may be screened up to 6 weeks prior to baseline visit. As per the study visit schedule screening will entail evaluation of:

- Inclusion and exclusion criteria
- Demographic data including age, assigned sex at birth, and race
- 2010 ACR/EULAR RA classification criteria
- Systemic disease assessment (RA involvement)
- Medical history
- Procedures history
- Allergies
- Concomitant medication
- DMARD therapy
- Corticosteroid therapy
- Clinical examination
- Rheumatoid Factor (RF) and Anti-CCP antibodies (CCP)a
- Routine blood tests (ESR, CRP, Full blood count (Haemoglobin, Red Cell Count,

- Haematocrit, White Blood Counts + differential including lymphocytes and
- neutrophils, Platelet count) liver function tests (ALT, AST), Kidney function/U&E (urea, sodium, potassium, creatinine, eGFR)b
- Total cholesterol, HDL, LDL, and triglycerides
- Hepatitis serology, HIV and IGRAc
- Vital signs
- Chest X-rayd
- ECG
- Pregnancy teste
- Joint assessment
- ACR-core set measures
- DAS 28 assessment
- Clinical Disease Activity Index (CDAI)
- VAS Pain score
- US assessmentf

Note: Anti-TNF therapy screening to include TB screening (IGRA), screening for Hepatitis and HIV according to local guidelines.

a RF/CCP tests should be performed unless these tests have been done previously and do not need repeating as per local guidelines.

b Routine blood tests do not need to be taken if the patient has already had these performed within 3 weeks of the screening visit

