c Hepatitis B screening must be performed unless it has been done in the preceding 3 months of the screening visit. If core antibody result is positive but the surface antigen and the viral load result is negative it is assessed as indicating a 'negative' overall result and therefore result is deemed as negative. TB (IGRA), Hepatitis C, and HIV screening is not mandatory; however, all centres are expected to act according to local guidelines with respect to patient screening prior to Anti-TNF and sarilumab therapy.

dA chest x-ray must be performed as screening for tuberculosis prior to biological therapy. A chest x-ray must be done at the screening visit to confirm the patient's eligibility, unless a chest X-Ray has been done in the preceding 3 months of the screening visit and the patient must not have had any pulmonary symptoms since then.

eA pregnancy test will be performed at each study visit for female patients of childbearing age irrespective of the use of contraceptive methods.

fUS assessment will be of the joint selected for biopsy to ensure that there is sufficient thickening to meet the following inclusion criterion: selected joint for biopsy must be minimum grade 2 synovial thickening, as assessed at the biopsy visit. This scan will not be reviewed centrally and is optional and not required if the site is confident that the joint will show sufficient inflammation at the biopsy visit.

Note: examples of reliable forms of contraception during the trial are: oral contraceptive and condom, intra-uterine device (IUD) and condom, diaphragm with spermicide and condom. Patients should continue to use a reliable form of contraception for 3 months after their last treatment if on sarilumab, or 3 weeks after their last treatment if they are on etanercept. Males with a partner of childbearing potential, will also be asked to use contraception for the duration of the study.

Note: a woman is considered of childbearing potential (WOCBP) i.e. fertile, following menarche (first occurrence of menstruation) and until becoming post-menopausal unless permanently sterile. Permanent sterilisation methods include hysterectomy, bilateral salpingectomy and bilateral oophorectomy.

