#### 9.2 Local laboratories

Bloods (RF & CCP, haematology, biochemistry panel, ESR, CRP, Hepatitis serology, HIV, IGRA, as described in the Schedule of Assessments Table) will be analysed at the patient's local hospital, as per local guidelines.

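### Section 7.5.1 keeps text for drugs not given in this trial, and so disagrees with the schedule on IGRA, hepatitis C and HIV testing and with the 14-week contraception rule for men

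*Protocol*

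**What the plan says.** The trial gives abatacept or placebo, each with methotrexate (section 1.3), and section 11.15.1 bars any other DMARD.

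**Infection screening.** Section 7.5.1 lists hepatitis serology, HIV and IGRA among the visit 1 evaluations and adds a note: "Anti-TNF therapy screening to include TB screening (IGRA), screening for Hepatitis and HIV according to local guidelines". Footnote c to that list keeps hepatitis B testing compulsory unless done in the previous 3 months. For the other tests it says: "TB (IGRA), Hepatitis C, and HIV screening is not mandatory; however, all centres are expected to act according to local guidelines", and it completes the sentence "with respect to patient screening prior to Anti-TNF and sarilumab therapy". The schedule in section 7.2 has a row "Hepatitis serology, HIV, IGRA" marked at visit 1. Its footnote i puts hepatitis B, IGRA, hepatitis C and HIV under one rule: screening "must be performed unless it has been done in the preceding 3 months of the screening visit or in line with local practice".

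Two other sections point to the schedule. Section 7.5 says "All trial activities and the visits at which they should be undertaken are documented in the" schedule of assessments, and section 9.2 lists, for the local laboratories, "Hepatitis serology, HIV, IGRA, as described in the Schedule of Assessments Table".

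**Contraception.** The opening of 7.5.1 reminds men and women to use contraception during the study and for an appropriate time after treatment stops. The later note in the same section gives 3 months for sarilumab and 3 weeks for etanercept, and asks men with a partner of childbearing potential to use contraception for the duration of the study. Section 11.17 sets up to 14 weeks after the last abatacept dose for women and men, and section 4.4 repeats it for men. Exclusion 25 requires cover beyond the end of treatment, for the period in the SmPC.

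**The concern.** Section 7.5.1 is the procedural text that a site has in hand when it screens and counsels a patient. In two places it is written for other drugs, and what it says there differs from the rest of the protocol.

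On screening, a site is told in one place that three infection tests before a biologic are not compulsory, and in another that they must be done. At stake is whether two eligibility criteria can be verified before abatacept or placebo starts. On contraception, the note gives no period for the drug under study, and its sentence for men contains no cover after treatment. Both are matters of participant safety and eligibility checking. Neither touches the estimate or its precision.

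**Working it through.** The plan gives no figure to reproduce. The check sets the texts side by side.

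**1. Are the named drugs part of the trial?** No. Sarilumab and etanercept appear only in 7.5.1. Anti-TNF treatment appears elsewhere as background, within the abatacept indication, or for the separate Precis-The-RA sub-study. None of these explains its use in the visit 1 notes.

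**2. Do the two screening footnotes agree?** The closing words of footnote i allow two readings. Under A, local practice settles when an earlier result counts. Under B, local practice may leave a test out.

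| Test | 7.5.1 footnote c | Footnote i, reading A | Footnote i, reading B |
|---|---|---|---|
| Hepatitis B | required | required | may be omitted |
| IGRA | not required, local guidelines | required | may be omitted |
| Hepatitis C | not required, local guidelines | required | may be omitted |
| HIV | not required, local guidelines | required | may be omitted |

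Under A, 3 of the 4 tests differ. Under B, those three agree, but hepatitis B differs, so 1 of 4. The footnotes disagree on either reading, because footnote i treats all four tests alike and footnote c splits off hepatitis B. In addition, the local guidelines that footnote c points to are those for drugs that no participant receives.

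**3. Which eligibility criteria need the results?**
- Exclusion 14 (latent TB without completed prophylaxis) needs the IGRA. The chest X-ray is compulsory in both places, but it does not replace IGRA for latent infection.
- Exclusion 11 is worded in terms of testing positive for hepatitis A, B or C. A patient with no hepatitis C test cannot meet it, so that part of the criterion would be passed by default. Its hepatitis B part is safe under footnote c.

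**4. Would a later step catch a missing result?** Under 7.3 the trial office confirms eligibility from the data recorded, and 15.5 has visit 1 and 2 data cleaned before randomisation. Section 14.13 lets a site enter an assessment as not done, with a reason. A site could give footnote c as that reason, and nothing in 7.3 says that such an entry stops randomisation.

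**5. Contraception after the last dose.**

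| Place | Women | Men |
|---|---|---|
| 7.5.1, opening | appropriate period, no number | appropriate period, no number |
| 7.5.1, note | periods for sarilumab and etanercept only | duration of the study |
| Exclusion 25 | as in the SmPC | as in the SmPC |
| 4.4 | not covered | up to 14 weeks |
| 11.17 | up to 14 weeks | up to 14 weeks |

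For women the note is silent on abatacept. For men it states a different rule from 4.4, 11.17 and exclusion 25, and from the opening of its own section.

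**The case against.** The strongest reply is that this is leftover text with the right rule close by. Both footnotes leave something to local practice. Section 7.5.1 itself lists the three tests as part of screening, and its note says that they are to be included. Sections 7.5 and 9.2 send the reader to the schedule, and the trial office checks eligibility before randomisation. On contraception, the sarilumab and etanercept periods apply to no participant and so cannot contradict 14 weeks. The opening of 7.5.1, exclusion 25, 4.4 and 11.17 together give the right rule for both sexes.

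Much of this stands, and it limits the point in four ways.
- A reader might infer that the two footnotes give the tests flatly opposite status. The closing words of footnote i do not allow that. The supported statement is that the footnotes are inconsistent and that one is ambiguous.
- A reader might add exclusion 10 to the criteria affected, since it names hepatitis C and HIV. It begins "Subject has a history or known presence of recurrent or chronic infection", so it can be applied without a new test result.
- A reader might see a conflict in footnote c's rule that a positive hepatitis B core antibody with negative surface antigen and viral load counts as negative. Exclusion 11 adds a condition of normal transaminases. Both can be followed together, and ALT and AST are measured at screening.
- A reader might put a number of weeks on the gap in male contraception. That depends on when the study ends for a participant, which the note does not say. Under section 14.3, six months after the last patient's final visit, there is no gap. No section ends the study at the last dose, so a gap of the full 14 weeks has no support.

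The reply does not remove the core. Having the right rule elsewhere shows that the protocol disagrees with itself, and 7.5.1 does not say which text prevails. Removing local discretion over tests is a policy choice in a multi-country trial, but exclusions 11 and 14 already presuppose the hepatitis C and latent TB results.

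**Conclusion.** The point holds as a correction that should be made. Section 7.5.1 refers to drugs outside the trial. Its footnote c is inconsistent with schedule footnote i on IGRA, hepatitis C and HIV, and a site following it could enrol without the results that exclusion 14 and the hepatitis C part of exclusion 11 require. The contraception note lacks an abatacept period, and its sentence for men is inconsistent with 4.4, 11.17 and exclusion 25.

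The size is three of the four tests, one exclusion criterion and part of a second. The first count takes footnote i as requiring the tests; if it allows omission, the disagreement moves to hepatitis B. The protocol does not say whether any site's local practice omits a test, so no number of participants is claimed out of the 200 planned. The sample size and the primary comparison of Group 1 with Group 3 are unaffected.

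**What to change.** - Delete the anti-TNF, sarilumab and etanercept text from 7.5.1.
- Reword 7.5.1 footnote c to match schedule footnote i: hepatitis B, hepatitis C, HIV and IGRA results, from screening or the preceding 3 months, are required before randomisation.
- Reword the end of footnote i so that local practice cannot be read as permission to leave a test out.
- State in 7.5.1 that women and men use contraception up to 14 weeks after the last dose, as in 11.17.

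The trial office can look for the four results when it confirms eligibility under 7.3. The cost is a text amendment, notice to sites, and the extra test at any site that now omits one. The tests are already scheduled at visit 1, so other sites have nothing to add.

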#### 7.5.2 Biopsy visit and randomisation (visit 2)

All Patients in the main study will receive a synovial biopsy (refer to 3TR Synovial Biopsy SOP) between 1 to 3 weeks prior to their baseline visit. Patients will have the following assessments recorded prior to the synovial biopsy at this visit:

- Concomitant medication
- DMARD therapy
- Corticosteroid therapy
- Routine blood tests (ESR, CRP, Full blood count (Haemoglobin, Red Cell Count, Haematocrit, White Blood Counts + differential – including lymphocytes and neutrophils, Platelet count) liver function tests (ALT, AST), Kidney function/U&E (urea, sodium, potassium, creatinine, eGFR)a
- Study specific bloods
- Vital signs
- Pregnancy test in female patients of child bearing potential b
- Joint assessment c
- DAS 28
- CDAI
- ACR-core set measures
- VAS Pain Score
- Pre Biopsy Assessment Form
- Adverse events
- Ultrasound examination of the patients' joints prior to the synovial biopsy
- Pre-baseline synovial biopsy d
- Randomisatione

a Routine blood tests do not need to be taken if the patient has already had routine blood tests performed within 3 weeks of the biopsy visit.

b A pregnancy test will be performed at each study visit for female patients of child-bearing age irrespective of the use of contraceptive methods

c Joint assessments and VAS physician assessment are only required to be completed by the blinded joint assessor from the baseline visit onwards. If possible, the same assessor should perform the joint count at all (pre- and post-randomisation) visits from baseline to ensure consistency.

d A synovial biopsy prior to baseline is mandatory for patients in the main study as part of the patient stratification process.

e Randomisation see section 7.4

#### 7.5.3 Biopsy visit and randomisation (visit 3)

Patients will receive Abatacept or placebo at their baseline visit depending upon randomisation and/or the treatment allocation algorithm. All assessments should be performed prior to the commencement of therapy. Patients at baseline will have the following assessments:

- Concomitant Medication
- DMARD therapy
- Corticosteroid therapy

- Clinical examination
- Cardiovascular risk assessment
- Routine blood tests (ESR, CRP, Full blood count (Haemoglobin, Red Cell Count, Haematocrit, White Blood Counts + differential – including lymphocytes and neutrophils, Platelet count) liver function tests (ALT, AST), Kidney function/U&E (urea, sodium, potassium, creatinine, eGFR)
- Vital signs
- Pregnancy test in women of childbearing potential a
- Joint assessment
- ACR core set measures
- Disease activity core data set (DAS28)
- Clinical Disease Activity Index (CDAI)
- VAS Pain score
- Physical function using the Health Assessment Questionnaire (HAQ)
- SF-36v2© (Licenced by Quality Metric Incorporated)
- FACIT Fatigue Questionnaire
- EQ-5D-5L
- Post Biopsy Assessment Form
- Adverse events
- Plain X-rays of hands and feet b
- Ultrasound assessment
- Optional urine, stool and saliva samples

All baseline assessments should be done within a +/- 7 day window

a A pregnancy test will be performed at each study visit for female patients of child bearing age irrespective of the use of contraceptive methods

b Plain X-rays of hands and feet do not need to be redone if the patient has already had them within 8 weeks of the baseline visit.

